### 7.1 Efficacy of RTS,S/AS01

RTS,S/AS01, the world's first malaria vaccine, was evaluated in a phase 3 trial in 15,459 infants (6-12 weeks old at the time of dose 1) and young children (5-17 months old at the time of dose 1) in 7 sub-Saharan African countries. Three doses of RTS,S/AS01 generated protection against clinical malaria which, though moderate compared with the efficacy achieved by vaccines against common viral diseases, is substantial in the context of malaria where there is a very high burden of disease and available interventions cannot offer high levels of protection (table 1). In the 12 months following completion of the primary vaccination course in children aged 5-17 months at the time of dose 1, the incidence of clinical malaria was reduced by 51% and the incidence of severe malaria was reduced by 44.5%. Protection appeared to wane over time: by 18 months after the primary vaccination course, efficacy was 46% against clinical malaria and 38% against severe malaria. Efficacy against clinical malaria of 3 doses alone declined in the successive 6-months periods from 68% in the first 6-month interval to 39% and 28% in the successive 6-month intervals. A fourth dose, given 18 months after dose 3, increased efficacy to 39% against clinical and 31.5% against severe malaria over the whole of the study (a median of 48 months follow-up) whereas, among the children randomised to receive only three doses of RTS,S/AS01, efficacy against clinical malaria fell to 26% and against severe malaria to -2.2%. The 4th dose of RTS,S/AS01 therefore appears to be needed to maintain efficacy against severe malaria.

Over the whole (median 4-year) follow-up of children in the phase 3 trial, vaccine efficacy was also confirmed against malaria hospitalization (37%, ATP, 95%CI 27-48.5), all-cause hospitalization (15%, ATP, 95%CI 6-25) and severe anaemia (62%, ATP, 95%CI 26.5-81). These benefits were demonstrated in the presence of high ITN coverage and where the identification and treatment of clinical and severe malaria episodes, as well as other medical care, was optimized. The enhanced access to good quality curative services likely limited disease progression and precluded the measurement of vaccine impact on mortality. However, modelling suggests a substantial potential survival impact of RTS,S/AS01 outside trial settings (1 life saved per 200 fully vaccinated children in moderate to high transmission settings).

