The MVPE will determine whether the introduction of RTS,S/AS01 leads to a reduction in child deaths, and a reduction in the incidence of hospital admission with severe malaria, over the 4 years of the implementation programme (MVIP, Malaria Vaccine Implementation Programme). The MVPE also addresses three safety signals that were observed in the phase 3 trial but whose significance was unclear: an unexplained excess of meningitis cases in RTS,S/AS01 recipients, an excess in cerebral malaria cases among RTS,S/AS01 recipients who developed severe malaria and, among the relatively small number of deaths that occurred in the trial, an excess of deaths among girls who received RTS,S/AS01 compared to girls who did not receive RTS,S/AS01. The data to be collected

¹ In the phase 3 trial, for every 1000 children vaccinated with 4 doses, a total of 1774 (95% CI 1387–2186) cases of malaria, 40 (95% CI 19–64) hospital admissions due to malaria, and 19 (95% CI 4 to 35) cases of severe malaria, were averted over about 4 years.

over 4 years will inform a policy decision about wider use of RTS,S/AS01 as a means to reduce malaria morbidity and mortality, when provided in addition to existing malaria control measures. It is anticipated that sufficient data to assess the safety signals are likely to be available after the first 2 years of the evaluation. At that time, all available data would be reviewed, including outcomes related to safety of the vaccine in routine use (meningitis, cerebral malaria, mortality by gender, AEFI), the impact on severe malaria and all-cause mortality, coverage of the first 3 doses, preliminary data on administration of the 4th dose, and cost-effectiveness assessment. A recommendation about wider use of the vaccine might therefore be made before final impact data are available, recognizing that the impact in any setting will depend on coverage and timeliness of vaccination and the malaria burden, which may differ from those in the MVIP [3].

2. Design of the evaluation

A total of 158 clusters, 66 in Ghana, 46 in Malawi and 46 in western Kenya, each cluster with a total population of about 100,000 on average, were randomized to either introduce RTS,S/AS01 vaccine in 2019 or to delay introduction until a decision is reached about safety and effectiveness.

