In the phase 3 trial, in children who received only three doses of RTS,S, the initial protection from severe malaria afforded by the vaccine was followed by a period in which their risk was increased compared to unvaccinated controls. This was thought to be a result of a reduced rate of acquisition of natural immunity in RTS,S recipients which led to an increased risk of severe malaria when the protection from the vaccine waned. The resulting excess of severe malaria cases offset the number of severe cases that had been averted during the previous months such that by the end of the trial there was no overall benefit in terms of severe malaria among children who received only 3 doses. In contrast, children who received four vaccine doses had sustained protection from severe malaria. It therefore appeared from the phase 3 trial data that a fourth vaccine dose was necessary in order to reduce a child's overall risk of severe malaria over the 4 years of the evaluation, although there was some statistical uncertainty surrounding this conclusion [2,5]. Beyond 4 years, based on data from three of the Phase 3 trial sites where surveillance was maintained for a total of seven years, it appeared that the risk of severe malaria is very low [3]. The implication is that national immunisation programmes would need to ensure children receive the fourth dose of the vaccine in order to reduce the burden of severe malaria and any associated mortality but, as far as severe malaria is concerned, a fifth dose would be unlikely to be necessary.

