A test of interaction will be used to determine whether the effect of RTS,S on mortality differs by gender, separately in each country, and for all countries combined, using population A1 (children eligible for RTS,S). We will also investigate whether the interaction by gender differs according to age, by considering age-eligible children in age strata (under 18 months, and 18 months and above, and, as data accrues, above 2 yrs).

Table 9: Dummy table for mortality rates by gender

Outcome:	Comparator			RTS,S			Interaction P-value
	Girls	Boys	Rate ratio	Girls	Boys	Rate ratio	
Deaths	Rate (N/PYAR)	Rate (N/PYAR)		Rate (N/PYAR)	Rate (N/PYAR)		
Deaths (excl. injury)	Rate (N/PYAR)	Rate (N/PYAR)		Rate (N/PYAR)	Rate (N/PYAR)		

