The sex ratio of mortality varies by age. Newborn boys tend to have higher mortality than newborn girls, this relative advantage of girls tending to decrease later in infancy. Infant mortality rates tend to be higher in boys than girls, the sex difference in child mortality rates being less marked [18,19,20 p.72]. Estimates of sex differentials in childhood mortality published by the United Nations Population Division, showed that the average male:female ratio of age-specific mortality rates, for sub-Saharan Africa, based on data from surveys and censuses conducted in the 2000s, was 1.18 in infants and 1.03 in children 1-4yrs [20]. These patterns can vary, for example in Malawi, Ashorn *et al.* [21] found a 2-fold greater mortality risk in 1-2-year-old boys than girls in a cohort study of infants born to a group of 795 pregnant women. The male:female sex ratio of mortality rates tends to increase, in both infants and in children, as overall under-5 mortality decreases [18]. In infants, this trend is attributed to the fact that as overall under-5 mortality declines, early infant deaths, where girls have the greatest advantage, form a larger proportion of infant deaths. In children 1-4 years, this trend is attributed to a smaller proportion of deaths due to infection and a larger proportion due to non-infectious causes which are more common in boys. These patterns can change if girls have poorer access to treatment or nutrition than boys. These sex differences in mortality may be less evident in this analysis as we will exclude deaths in early infancy and deaths due to injury, but age, and the overall level of under-5 mortality, could be potential confounders in the assessment of the effect of RTS,S on the sex ratio of mortality. To explore these effects, the sex ratio of mortality will be compared between age groups and between areas with higher and lower overall levels of under 5 mortality, in each arm of the trial. And analyses of interaction by gender will be done with adjustment for age and for overall level of under-5 mortality.

As secondary analyses, other key outcomes will be also be analysed by gender (severe malaria; cerebral malaria; all cause admission to hospital).

Cerebral malaria

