In addition to the primary analysis of cerebral malaria, comparing incidence between intervention and comparator areas, we will compare effectiveness of vaccine introduction between cerebral malaria and other forms of severe malaria using a test of interaction. If cerebral cases tend to occur at older ages a lower effectiveness might be expected due to waning vaccine efficacy, to check for

this we will plot the age distribution of cerebral cases and non-cerebral severe cases in the vaccine-eligible age group, in each country.

Transmission intensity

In each country, clusters will be classified into higher and lower transmission strata, based on the prevalence of *P.falciparum* by RDT in the baseline surveys. For impact outcomes, to allow for potential imbalance in age distribution of severe malaria between intervention and comparator areas, we will adjust for transmission stratum, as a secondary analysis. Impact for the non-malaria-specific outcomes (all cause mortality, all cause admission) will also be estimated separately in each stratum and a test of interaction will be done.

20. Statistical methods for estimating rates, rate differences and rate ratios

The layout of the data from each cluster and calculation of rate ratios and rate differences is as set out in the table below. n is the number of events, for example $n_{0,1,A}$ is the number of events in group A in cluster 1 in the comparator group (group 0), and $T_{0,1,A}$ is the corresponding person time. The totals in each arm are denoted by $n_{1,A}$ and $n_{1,B}$ (arm 1 = RTS,S) and $n_{0,A}$ and $n_{0,B}$ (arm 0 = comparator). Stata code to estimate rate ratios and differences is given in Annex 2.

Table 10: Calculation of rate ratios and rate differences

Country	Intervention	Cluster	Group A (events, person time)	Group B (events, person time)	Rate ratio (A/B) in each area	Difference between log rate ratios	Rate difference (A-B) in each area	Difference between rate differences
Ghana	RTS,S	1	$n_{1,1,A}$ $T_{1,1,A}$	$n_{1,1,B}$ $T_{1,1,B}$	$R_1 = (n_{1,A}/n_{1,B}) \times (T_{1,B}/T_{1,A})$		$d_1 = n_{1,A}/T_{1,A} - n_{1,B}/T_{1,B}$	
	RTS,S	2	$n_{1,2,A}$ $T_{1,2,A}$	$n_{1,2,B}$ $T_{1,2,B}$				
				
		TOTAL	$n_{1,A} = \sum n_{1,i,A}$ $T_{1,A} = \sum T_{1,i,A}$	$n_{1,B} = \sum n_{1,i,B}$ $T_{1,B} = \sum T_{1,i,B}$				
	Comparator	1	$n_{0,1,A}$ $T_{0,1,A}$	$n_{0,1,B}$ $T_{0,1,B}$				
	Comparator	2				
				

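### The supplementary test of cerebral against other severe malaria has no age adjustment, so waning could bias it modestly if cerebral cases are older

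*SAP*

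**What the plan says.** SAP Section 19 (Subgroup analyses, Cerebral malaria) adds to the primary incidence comparison: "we will compare effectiveness of vaccine introduction between cerebral malaria and other forms of severe malaria using a test of interaction". It then names the difficulty: "If cerebral cases tend to occur at older ages a lower effectiveness might be expected due to waning vaccine efficacy". Its response is "this we will plot the age distribution of cerebral cases and non-cerebral severe cases in the vaccine-eligible age group, in each country". Neither that section, Section 20 nor Annex 3 gives age strata, an age-adjusted estimate or a rule for acting on the plot. The transmission-stratum adjustment described next in Section 19 is a secondary analysis of impact outcomes and concerns age imbalance between arms, which is a different problem.

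The gender interaction in Section 19 is treated differently. Its variation with age is examined "by considering age-eligible children in age strata (under 18 months, and 18 months and above", with a stratum above 2 years as data accrue, and "analyses of interaction by gender will be done with adjustment for age and for overall level of under-5 mortality".

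**The concern.** The first three doses are scheduled between 5 and 9 months of age, with no catch-up in Ghana or Malawi and first doses up to 12 months in Kenya. Age therefore tracks time since vaccination closely, and efficacy changes with that time. SAP Section 9 says that in three-dose children the early protection "was followed by a period in which their risk was increased compared to unvaccinated controls". Protocol 7.1 reports that, over the whole phase 3 study, "among the children randomised to receive only three doses of RTS,S/AS01, efficacy against clinical malaria fell to 26% and against severe malaria to -2.2" per cent. Two outcomes with different age patterns will then show different crude rate ratios even if the vaccine acts identically on both.

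SAP Section 1 describes the phase 3 signal as "an excess in cerebral malaria cases among RTS,S/AS01 recipients who developed severe malaria", which is the relative contrast this test examines. Without a planned adjustment, a positive result is ambiguous: it may reflect age alone, or a real difference may be discounted by pointing at the plot. An adjustment chosen after seeing the data would be post hoc on a safety question.

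**Working it through.** **Reproducing the plan's own figures.** SAP Table 5 uses coverage c = 0.74 and contamination d = 0.04. The diluted ratio is (c·R + 1 − c) / (d·R + 1 − d).
- Cerebral malaria, R = 2.57: 2.162 after coverage, then 2.162/1.063 = 2.03 (SAP: 2.16 and 2.03).
- Severe malaria, R = 0.66: 0.748, then 0.748/0.986 = 0.76 (SAP: 0.75 and 0.76).
- Diluted phase 3 contrast, cerebral to severe: 2.03/0.76 = 2.67.

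The SAP prints no figure for the interaction test itself.

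**Severe malaria rate ratios by time since dose 1 (Protocol Table 1, by subtraction).**
- Months 2.5–14: (87/4358.3)/(80/2219.3) = 0.554.
- Months 14–20: (42/2020.7)/(25/1024.2) = 0.852. With so few events, the crude 95% interval is wide: about 0.52 to 1.40.
- After month 20, assigning half the pooled earlier events and person-time to each schedule: four doses (36.5/4270.1)/(52/4421.3) = 0.727; three doses (94.5/4411)/(52/4421.3) = 1.82.

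Diluted with c and d, these become 0.682, 0.895, 0.807 and 1.557. Clinical malaria efficacies of 68, 39 and 28% in successive six-month intervals (Protocol 7.1) give ratios 0.32, 0.61 and 0.72, diluted to 0.511, 0.723 and 0.802.

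**Spurious interaction.** Both outcomes receive the same effect in each window. The overall ratio for an outcome is Σ(case share × diluted window ratio), and the spurious interaction is the cerebral sum divided by the other-severe sum. The documents give no age distribution for cerebral cases, so the case shares are assumptions. The other-severe shares in rows 1, 2, 4 and 5 follow the phase 3 control events (80 of 105; 80, 25 and 52 of 157).

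| Windows | Other severe, % | Cerebral, % | Sums (cerebral / other) | Ratio |
|---|---|---|---|---|
| 1. Severe, to month 20 | 76/24 | 56/44 | 0.776/0.733 | 1.06 |
| 2. Severe, to month 20 | 76/24 | 36/64 | 0.819/0.733 | 1.12 |
| 3. Clinical, three intervals | 50/30/20 | 20/30/50 | 0.720/0.633 | 1.14 |
| 4. Severe, four doses | 51/16/33 | 31/16/53 | 0.782/0.757 | 1.03 |
| 5. Severe, three doses only | 51/16/33 | 31/16/53 | 1.180/1.005 | 1.17 |

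**Larger values.** Take shares of 60/20/20 for other severe and 35/20/45 for cerebral, with half the children on each schedule (post-month-20 ratio about 1.28). The undiluted sums are 0.940 and 0.759, a ratio of 1.24. At 74% coverage this is 0.956/0.822 = 1.16. With no fourth doses it is 1.26; with all fourth doses, 1.04.

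**Ceiling with no age overlap.** Severe windows to month 20: 0.895/0.682 = 1.31. Clinical windows: 0.802/0.511 = 1.57. If efficacy wanes fully to zero: 1.47 and 1.96 respectively. All early cases against all three-dose rebound cases: 1.557/0.682 = 2.28. None reaches 2.67.

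**Effect on a nominal 5% test.** Assume 100 to 400 eligible cerebral cases, nine times as many other severe cases (from 400 against 4000 in Table 5, so 3600/400), and Poisson counts without between-cluster variation. For row 2 at 400 cases the cells are 180, 220, 1523 and 2077. The standard error is √(1/180 + 1/220 + 1/1523 + 1/2077) = 0.106 and log 1.116 = 0.110, which gives a rejection rate of about 18%. Across 100 to 400 cases the rates are 6–8%, 8–18%, 9–23%, 5–6% and 12–33% for rows 1 to 5.

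A comparison made within these windows has a ratio of 1.00 by construction.

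**The case against.** A reader might infer that waning alone could reproduce the cerebral malaria safety signal. The documents do not support that. The primary safety estimate is the cerebral malaria incidence rate ratio in group A1, and waning moves it towards 1, not above it. Only rebound could raise it above 1 (1.18 in row 5), and that would be a real change in incidence, not an artefact of missing age adjustment. SAP Section 8 also starts from evidence of increased incidence, then checks vaccination status, case definitions, unrelated admissions and consistency across countries before any judgement of harm. This stands in full.

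A reader might also infer that the test cannot answer its question. That too goes beyond the text. The SAP raises older age only as a possibility, and if the two age distributions coincide there is no bias. The crude contrast is also a legitimate summary of population-level effectiveness. It simply cannot separate a cerebral-specific effect from age.

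The larger magnitudes are open to challenge. The intermediate analysis is anticipated at about month 24. With steady births, the share of eligible person-time more than 20 months after the first dose would then be about (4/24)² = 3% in Ghana and Malawi, and none in Kenya, which started in September 2019. By month 46 it is about (26/46)² = 32%. The no-fourth-dose figures do not describe the planned programme.

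Two objections to simple stratification also stand. Comparing case ratios between arms in eligible children alone discards group B, which SAP Section 6 uses to remove differences in diagnostic performance. The cells could also be sparse. Table 5's 300 cerebral cases for 80% power count both eligibility groups. If 25% are eligible (assumed), 75 cases over three countries, two arms and two strata average about six per cell.

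**Conclusion.** The concern holds for the supplementary interaction test only. The SAP identifies the confounder, handles the same problem by adjustment for gender, and here plans only a plot. The bias depends on cerebral cases being older, which the documents neither show nor rule out. On moderate assumed shifts it is a ratio of about 1.03 to 1.17. It is near the bottom of that range if four doses maintain the effect and near the top with three-dose rebound. Beyond that it needs both a large shift and many cases in children without a fourth dose. These figures also rest on imprecise phase 3 window ratios and on an even split of early events between schedules. The primary cerebral malaria analysis is not called into question.

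**What to change.** Pre-specify an age-adjusted version of this interaction and report it with the crude test and the age plot.

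- For vaccine-eligible cases, use the gender strata: under 18 months, 18 months and above, and above 2 years as data accrue.
- Keep the cerebral:non-cerebral ratio in group B as the correction for diagnostic differences between arms, as the double ratio in Section 20 does for gender.
- Where stratum-by-country cells are sparse, do not pool stratum log ratios. Fit one model with cluster-robust standard errors to all severe malaria cases, with cerebral versus other as the outcome and terms for country, age stratum, arm, eligibility group and arm by eligibility. The last term is the age-adjusted log interaction ratio.
- Base any statement of a cerebral-specific difference on the age-adjusted estimate.

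Age is already recorded for every admission, so the cost is SAP wording and some code. The interval will be wider, and broad strata leave some waning within them: the group aged 18 months and above mixes late waning, the fourth dose and rebound.
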